4.2. Inclusion Criteria

Up to 54 subjects with atopic dermatitis will be enrolled in this study. Enrollment will not take race or gender into consideration. Pregnant women, children (under age 18), and unhealthy subjects with significant co-morbid conditions as determined by the PI will be excluded.

1. Male or female subjects who are not pregnant or lactating. Female subjects of child-bearing potential must have a negative urine pregnancy test on the day of the screening visit in order to be eligible for the study.
2. 18-60 years of age
3. Diagnosis of atopic dermatitis for at least 6 months using the Hanifin and Rajka Diagnostic Criteria for atopic dermatitis
4. Presence of lesional atopic dermatitis skin in both antecubital fossae
5. Positive *S. aureus* colonization based on results of a skin culture taken from one of their AD-affected antecubital fossae during the screening visit
6. Positive for antimicrobial CoNS species from non-lesional AD skin

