8.2. Screening/Baseline Visit

The purpose of the screening period is to confirm eligibility to continue in the study.

1. The following procedures, assessments, and laboratory measures will be conducted to determine participant eligibility: Prior to beginning any study procedures, subjects will first be asked to review and sign the informed consent form.
2. After obtaining informed consent, the inclusion/exclusion criteria will be reviewed.
3. A brief medical history and physical exam/vital signs will be performed to assess whether the subject meets the required criteria for the study.
4. Female subjects of child-bearing potential will complete a urine pregnancy test while in the office to ensure that they are not pregnant.

[figure not shown]
5. Patients who meet the inclusion and exclusion criteria will then have their lesional AD skin scored according to the localized SCORAD grading scale, and the extent of AD lesional skin on their bilateral arms will be recorded.
6. A skin swab performed on the lesional atopic dermatitis skin of their antecubital fossae, will be performed to detect the presence of *S. aureus*.

Subjects who do not meet the inclusion/exclusion criteria due to the application or use of prohibited medications within the timeframe noted will be considered screen-failures. Skin swabs of these patients will not be performed. These subjects may return for another screening visit after completing the necessary wash-out period (7 days for topical medications, 28 days for oral medications) if they are interested in doing so. Subjects eligible for this study will be randomized at the Treatment visit 1 to either AMT cream or placebo in a 2:1 allocation ratio (AMT cream: placebo).

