8.3. Study Visits or Study Assessments

Aim: To determine the change in abundance of *Staph aureus* from baseline after 1 week BID application of AMT.

The study flowchart is provided below:

This experiment will consist of up to 9 office visits (Screening, Treatment, 2 optional visits, and 5 Follow-up visits) and two phone calls. All office visits will occur at the UCSD Dermatology Clinic. Up to twenty seven (27) subjects with AD will be recruited for this study. The exact study procedures are noted below:

Screening Visit 1 (Day -60 to Day -2)

Prior to beginning any study procedures, subjects will first be asked to review and sign the informed consent form. After obtaining informed consent, the inclusion/exclusion criteria will be reviewed. A brief medical history, vital signs, and physical exam will be performed in helping to assess whether the subject meets the required criteria for the study. Female subjects of child-bearing potential will complete a urine pregnancy test while in our office to ensure that they are not pregnant. Patients who meet the inclusion and exclusion criteria

will then have their lesional AD skin scored according to the SCORAD grading scale, EASI, and modified EASI, and localized SCORAD, and the extent of AD lesional skin on their bilateral arms will be recorded. A skin swab will be performed on the lesional atopic dermatitis skin of their antecubital fossae bilaterally to detect the presence of *S. aureus*. Additionally, we will take four (4) culture swabs from the subject's non-lesional (no AD) skin on their upper arms. These culture swabs will be placed in tryptic soy broth (TSB) until processed in the lab, where they will be used to grow the subject's antimicrobial peptide-producing *Staph* species to use for the autologous microbiome transplant. Subjects will then receive a bar of Dove moisturizing soap, which they will be instructed to use whenever they shower until after the follow-up visit is complete. This will conclude the screening visit. The total time for this visit will be approximately 40 minutes.

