ensure that they are not pregnant. Vital signs will be taken. Two (2) skin culture swabs total will be taken of their lesional antecubital fossae to assess for *S. aureus*. Additionally, four (4) skin culture swabs will be taken of their non-lesional skin to assess for antimicrobial *CoNS*. These culture swabs will be placed in tryptic soy broth (TSB) until processed in the lab, where they will be used to grow the subject's antimicrobial peptide-producing *Staph* species to use for the autologous microbiome transplant. This will conclude the repeat culture visit. The total time for this visit will be approximately 20 minutes.

Repeat phone call, as necessary (Day -30 to -1)

Subjects will be notified via telephone whether or not their skin swabs grew *S. aureus* and whether they have antimicrobial *Staphylococcus* species present. Subjects with a skin culture positive for *S. aureus* and antimicrobial coagulase-negative *Staph* (*CoNS*) will be enrolled in the study. For these subjects, Visit 3 (Treatment visit) will be scheduled. Subjects with a negative *S. aureus* skin culture or are negative for *CoNS* will be identified as screen failures.

Visit 3, Treatment Visit (Day 0)

Eligible subjects with + *S. aureus* and *CoNS* screening cultures will be enrolled in the study and instructed to return to the clinic. This waiting period will allow laboratory staff to grow and prepare the subject's endogenous AMP-producing bacteria to be mixed with Cetaphil for application at the treatment visit. A laboratory staff member will serve as an unblinded pharmacist and once eligibility information is relayed to the unblinded pharmacist, the subject will be randomized to an allocation ratio of 2:1 (AMT cream: vehicle cream). The subject will be asked not to bathe, shower, or exercise on the day of the treatment visit, and also that the application of any topical products to their arms on this day is prohibited. Hand washing is allowed, but subjects will be instructed to take care not to apply soap or water above their wrists.

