This visit will begin by reviewing the subject's interim medical history, including medication history to ensure that he/she did not use any topical AD treatments on their arms or antihistamines within 7 days or oral AD treatments within 28 days of this visit. For all subjects, a focused physical exam will then be performed of the subject's bilateral arms to ensure that there is no evidence of cracks, breaks or infections of the skin on the arms. Vital signs will be taken. The localized SCORAD, modified EASI, global EASI and SCORAD grading scale will be used to rate the severity of the lesional AD skin on the subject's bilateral arms, and the extent of lesional AD skin on each arm will be recorded. Digital photographs of the lesional skin on both arms will be taken. Each photograph will also include a ruler so the scale of the lesions can be determined, as well as a card with the subject's identification number, visit date, and photograph location so that the photographs can be

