8.5. Visit Windows

Study visits should take place within the time limits specified below: the designated visit windows (*i.e.* +/- *n* days) for each scheduled visit are also indicated on the Table of Events

Table 1: Schedule of Events 2:1 randomization of AMT to placebo cream for 1 week of BID application

Study Procedures Visit (V)	V1	V2 (Phone 1) ^{a,b}	Repeat Culture Visit ^c	Repeat Phone Call ^d	V3 (Treatment)	Optional visit 1*	Optional visit 2*	V4 (Resupply)	V5 (End of Treatment)	V6	V7	V8	V9 (phone 2)
Day (D), visit window (d= day, h= hours)	D -60 to -2	D -59 to -1	D -31 to -2	D -30 to -1	D0	D0, 1 h after V4 +/- 2 h	D0, 4 h after V4 +/- 2 h	D 4 +/- 5d	D7 +/- 7d	D8 +/- 7d	D9 +/- 7d	D11 +/- 7d	D38 +/- 7d
Screening/Baseline:													
Informed consent	X												
Inclusion/ Exclusion	X	X	X	X	X								
Medical history/ demographics	X		X		X								
Physical exam	X		X		X								
Con meds/procedures	X		X		X			X	X	X	X	X	
Screening skin culture swabs	X		X										
Treatment:					X								
Apply AMT cream or vehicle cream					X								
Dispense IP						X		X					
Dispense Subject Diary						X		X					
Returned unused creams								X	X				
Collect Subject Diary								X	X				
Efficacy:													
Skin swabs						X	X	X	X	X	X	X	
SCORAD	X					X		X	X	X	X	X	
EASI	X					X		X	X	X	X	X	
Photos	X		X		X			X	X	X	X	X	
Safety:													
Weight	X												
Height	X												
Vital Signs	X		X		X			X	X	X	X	X	
Skin exam	X		X		X	X	X	X	X	X	X	X	
Adverse events	X	X	X	X	X	X	X	X	X	X	X	X	
Testing													
Pregnancy test (urine)	X		X										

- Screened subjects who are + for *Staph aureus* and *CoNS* will be contacted via telephone to schedule their treatment initiation Day 0 visit.
- Subjects who are negative for *Staph aureus* and/or *CoNS* and agree to medication washout will be contacted via telephone to schedule a repeat culture visit.
- Only subjects who are negative for *Staph aureus* and/or *CoNS* and agree to washout will return for a repeat culture visit.
- Only subjects who complete the repeat culture visit will have a repeat phone call.
- Only subjects who agree to participate in optional visits, as indicated on their informed consent form, will complete this visit.

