12.6 Pregnancy Reporting

The investigator shall be informed immediately of any pregnancy in all study subjects or a partner of a study subject. A pregnant subject shall be instructed to stop taking study medication. The investigator shall counsel the subject and discuss the risks of continuing with the pregnancy and the possible effects on the fetus. Monitoring of the pregnant subject shall continue until the conclusion of the pregnancy.

The investigator will report to NIAMS within 1 business day of notification of the event.

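### No pregnancy test is scheduled on Day 0: the last one before randomisation and first dose is 2 to 60 days old (2 to 31 if re-cultured), so an unrecognised or undisclosed pregnancy could pass

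*Combined protocol and SAP*

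**What the plan says.** The exclusion is plain. Section 4.2 states: "Pregnant women, children (under age 18), and unhealthy subjects with significant co-morbid conditions as determined by the PI will be excluded". Inclusion 1 then sets the test: "Female subjects of child-bearing potential must have a negative urine pregnancy test on the day of the screening visit".

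Testing is scheduled at two points. Section 8.3 has a urine test at Screening Visit 1 and another at the Repeat Culture Visit. The second visit is only for subjects whose first culture was negative for *S. aureus*, for antimicrobial CoNS, or for both, and who agree to wash out. The pregnancy-test row of Table 1 (section 8.5) carries two entries, which agree with the visit text.

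Randomisation comes later. Section 8.2 says: "Subjects eligible for this study will be randomized at the Treatment visit 1". Section 8.3 places this, and the first application of cream, at Visit 3 on Day 0. Of the checks that day it says: "This visit will begin by reviewing the subject's interim medical history, including medication history". It goes on to an examination of the arms, vital signs, severity scores, photographs and swabs. It lists no pregnancy test.

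For a pregnancy found after dosing has begun, section 12.6 says: "A pregnant subject shall be instructed to stop taking study medication". It also requires monitoring until the pregnancy ends and a report to NIAMS within 1 business day.

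**The concern.** Pregnancy status can change between screening and dosing, so a criterion confirmed only at screening may no longer hold when it matters. Subjects whose first cultures are positive go from Visit 1 to Visit 3 with no retest, and theirs is the route with the longest permitted interval.

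At stake is whether eligibility is verified on the day live bacteria are first applied in a phase 1 trial. A pregnancy detectable on Day 0 would come to light before exposure if it were tested for then. As scheduled, it may surface only during the 7-day course or afterwards, when section 12.6 takes over.

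**Working it through.** The plan gives no figure for this interval, so there is none to reproduce. The check is day arithmetic on the visit windows, followed by a comparison of sections.

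**Inputs**
- Visit 1: Day -60 to Day -2 (section 8.3, Table 1)
- Repeat Culture Visit, as needed: Day -31 to Day -2 (section 8.3, Table 1)
- Randomisation and first application: Day 0 (sections 8.2 and 8.3)
- Washout of oral AD therapy: 28 days before the Treatment visit (section 4.3, item 3)

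**Age of the last scheduled test at first dose** = Day 0 minus the day of that test.

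| Route | Last test | Shortest | Longest |
|---|---|---|---|
| First cultures positive | Visit 1 | 0 - (-2) = 2 days | 0 - (-60) = 60 days |
| Re-cultured | Repeat Culture Visit | 0 - (-2) = 2 days | 0 - (-31) = 31 days |

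**Subjects on prohibited medication at screening.** Two sections give different routes.
- Section 8.2 makes them screen failures, takes no swabs, and lets them come back for a new screening visit after washout. The section 8.2 procedures include a urine pregnancy test, so these subjects are retested after washout.
- Section 8.3 lets those who agree to wash out be swabbed at Visit 1. If both cultures are positive they proceed to Visit 3. A subject still taking oral therapy at Visit 1 then needs 28 clear days before Day 0, so Visit 1 can be no later than Day -28. The test is then at least 0 - (-28) = 28 days old and at most 60.

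Whether a gap of four weeks or more is built in for these subjects therefore depends on which section governs.

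**What Visit 3 can establish without a test.** Table 1 marks an inclusion/exclusion review and a medical history at Visit 3.
- Pregnancy known and reported: caught.
- Pregnancy known but not disclosed: not caught.
- Pregnancy not recognised, because it began after the earlier test or was too early for it: not caught.

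**Comparison with the other criteria.** Section 4.3 anchors its other time-sensitive items to the Treatment visit: topical AD treatment, antihistamines, systemic AD therapy, bleach baths, antibiotics and immunosuppressants (items 1, 2, 3, 5, 13 and 14). Skin integrity is re-examined on Day 0. Pregnancy is not rechecked by test that day, although retesting at the Repeat Culture Visit shows that the plan accepts that a first result ages.

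**The case against.** The plan is consistent about the test. Inclusion 1 places it at screening, and the visit text and Table 1 carry that out, so this is a design choice and not an execution error. The product is described as the subject's own skin bacteria applied topically, no pregnancy-specific hazard is stated, and section 12.6 has a procedure for a pregnancy that arises. The windows also permit an interval as short as 2 days. All of this stands, and it limits the weight of the point. It does not supply a current result on Day 0.

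Stronger readings are tempting, but the documents do not support them.

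- *Any subject who has become pregnant could be randomised.* The Visit 3 history and eligibility review would exclude a subject who knows and says so.
- *A pregnancy would cost one of 27 subjects.* Sections 3.1 and 11.3 replace those who withdraw. Section 12.6 requires study medication to stop but does not require withdrawal from the study. The intention-to-treat set in section 13.4.1 keeps anyone with a follow-up visit after intervention. Section 13.7 already allows for 20% drop-out.
- *Everyone on oral therapy waits 28 days without a retest.* That follows from section 8.3 only; section 8.2 says otherwise.
- *Contraception is left unaddressed.* The consent pages were not in the text reviewed and may cover it, so the point is given no weight.

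A Day 0 urine test can also miss a very recent conception. It would narrow the gap without closing it.

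**Conclusion.** The point holds in limited form. The plan excludes pregnancy but schedules no test at the visit where subjects are randomised and first dosed. The exposure is confined to unrecognised or undisclosed pregnancies. The documents do not give the number of subjects affected. It is likely small, and no rate is assumed here.

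This is a matter of eligibility verification and subject safety. It does not touch the sample size, the primary endpoint or its analysis. The conclusion rests on the stated visit windows and on reading the two entries in the Table 1 pregnancy row as Visit 1 and the Repeat Culture Visit, which the visit text supports. The change is worth making because it is specific and cheap and brings pregnancy into line with the criteria already anchored to the Treatment visit.

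**What to change.** 1. Add a Visit 3 (Day 0) entry to the pregnancy-test row of Table 1. Add the urine test to the Visit 3 text in section 8.3, to be done before eligibility is relayed to the unblinded laboratory staff member for randomisation.
2. Amend inclusion 1 in section 4.2 to require a negative test both at screening and on Day 0 before randomisation.
3. Reconcile sections 8.2 and 8.3 on whether subjects on prohibited medication at screening return for a new screening visit after washout or can go on to Visit 3 from their first swabs.

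The cost is one more urine test for each female subject of child-bearing potential, at a visit already held and of a kind the protocol already uses. The drawbacks are a few minutes at that visit and an occasional late screen failure after a subject's batch has been prepared.

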4.3. Exclusion Criteria

Individuals who meet any of these criteria are not eligible for enrollment as study participants:

1. Use of any topical AD treatments (including topical steroids, topical calcineurin inhibitors) to either arm within one week of the Treatment visit
2. Use of any antihistamines 7 days within one week of the Treatment visit
3. Use of any oral/systemic AD therapies (steroids) within 28 days of the Treatment visit
4. Severe AD that would worsen significantly from holding a participant's usual topical/oral AD medications for the time periods required in the inclusion/exclusion criteria (one week prior to the

Treatment visit for topical medications and antihistamines and 28 days prior to Treatment visits for oral medications)

5. Subjects who have taken a bleach bath within a week prior to the Treatment visit, or who take bleach baths during the study
6. Patients with severe medical condition(s) that in the view of the investigator prohibits participation in the study
7. Subjects with Netherton's syndrome or other genodermatoses that result in a defective epidermal barrier
8. Any subject who is immunocompromised (e.g. provides researchers with a history lymphoma, HIV/AIDS, Wiskott-Aldrich Syndrome) or has a history of malignant disease (with the exception of non-melanomatous skin cancer). This information will be gathered verbally from the patient while taking a medical history from the patient, and will not involve further testing such as an HIV test.
9. Subjects with a history of psychiatric disease or history of alcohol or drug abuse that would interfere with the ability to comply with the study protocol
10. Active bacterial, viral or fungal skin infections
11. Any noticeable breaks or cracks in the skin on either arm, including severely excoriated skin or skin with open or weeping wounds suggestive of an active infection or increased susceptibility to infection.
12. Ongoing participation in another investigational trial
13. Use of any oral or topical antibiotic for up to four weeks prior to the Treatment visit
14. Use of any systemic immunosuppressive therapy (e.g. CsA, MTX, etc.) within four weeks of the Treatment visit.
15. Sensitivity to or difficulty tolerating Dove fragrance-free bar soap or Cetaphil lotion
16. Subjects with prosthetic heart valves, pacemakers, intravascular catheters, or other foreign or prosthetic devices.

5. Known and Potential Risks and Benefits to Participants

5.1. Risks of Investigational Product

Risk of applying microbial cream (Cetaphil® containing Staphylococcal bacteria)

Skin infection

The likelihood of subjects developing a skin infection is low given that we will be transplanting their non-pathogenic autologous bacteria that have antimicrobial peptide-producing abilities. Since we are transplanting the subject's own endogenous bacteria back onto them, we know that these bacteria are present on the subject's skin at baseline without causing an infection. In addition, the bacteria strains to be transplanted onto the patient will be screened prior to putting it into the AMT cream to ensure that it is not a skin pathogen. The known pathogen *S. aureus* that frequently colonizes AD skin will not even be considered as a potential bacteria to transplant because of its yellow color on mannitol-salt-agar plates, which isolated bacteria will be grown on. Only red colonies (*S. epidermidis*) growing on mannitol-salt-agar plates will be chosen and screened as potential bacteria to be transplanted onto the subject. If anything, we expect the population of *S. aureus* to be reduced with the use of the AMT cream, since the AMT cream will contain only bacteria that are known to inhibit *S. aureus*. Furthermore, we will be applying these bacteria topically and will exam all patients first to ensure that they do not have any cracks or excoriated skin on their arms before we apply it. We will also avoid applying the microbial cream to the hand since the hand would be a likely source of spreading these bacteria onto other surfaces that other people may contact. Should an infection occur (or should the subject be concerned about an infection), the subject should call [name] or [name]. The subject would be treated according to the standard treatment after examination by Drs. [name] or [name]. The treatment will include topical and/or oral antibiotics

(for infection) depending on the severity of the infection clinically, and Cetaphil® moisturizing lotion (for irritation and dryness), provided by Drs. [name] or [name]. The topical antibiotic of choice will be mupirocin. The oral antibiotic of choice will depend on the individual subject's medical history, including any possible contra-indications to certain medications due to allergies or other concomitant medication use, but doxycycline will be the first line oral antibiotic, followed by a cephalosporin or penicillinase-resistant penicillin.

If the subject calls to report a possible infection during a time when the clinic is closed, the subject will be directed to the closest urgent care facility for further management.

5.2. Risks of Study Procedures

Risk of loss of confidentiality: Every reasonable effort will be made to keep records confidential. Research records will be stored in a secure building under lock and key of the study personnel. Data stored in our computers are password protected. Unless required by law, only the Study Doctors, the Study Team, the UCSD Institutional Review Board, the Food and Drug Administration, and the National Institutes of Health (NIH) will have access to confidential data which identifies you by name. Because of the need to give these parties access to this information, absolute confidentiality cannot be guaranteed.

Withdrawal from Medications

Adverse events associated with stopping the use of protocol-prohibited medications may result in worsening of the condition being treated and reported as such. As listed in the inclusion/exclusion criteria, subjects with severe AD who may have difficulty tolerating periods without medication use will be excluded from participating.

Skin Swabs

There are no significant risks associated with taking swabs of the skin.

